5.5. Justification for Dose

Administration of single GLWL-01 doses of up to 600 mg QD in healthy subjects, and of multiple (up to 28 days) GLWL-01 doses of up to 600 mg BID in obese patients with type 2 diabetes was safe and generally well tolerated (GLWL-SMP study). Doses of GLWL-01 equal to or higher than 150 mg BID resulted in numerical decreases of plasma AG levels in obese patients with type 2 diabetes over 28 days, with the maximum decreases observed for the 450-mg BID dose group. Therefore, a 450-mg BID dosing regimen was chosen for this study as it has been demonstrated to be safe and to achieve target engagement.

6. Study Population

Prospective approval of protocol deviations to recruitment and enrollment criteria, also known as protocol waivers or exemptions, is not permitted.

6.1. Inclusion Criteria

Patients are eligible to be included in the study only if they meet all of the following criteria at screening:

1. Male and female outpatients between 16 and 65 years of age inclusive, prior to signing informed consent.
2. Confirmed diagnosis of PWS based on genetic confirmation using DNA methylation test.
3. Body mass index (BMI) of 27 to 60 kg/m², inclusive, at Visit 1.
4. No evidence of weight excursion beyond 10% of baseline weight within 3 months prior to Visit 1 (self- or caregiver-reported).
5. Patients must provide assent and have a reliable caregiver (must have been caring for the patient for at least 6 months) who provides a separate written informed consent to participate. The caregiver is expected to be the primary caregiver throughout the study and must be in frequent contact with the patient (defined as at least 4 awake hours per day). The caregiver must be able to communicate with site personnel and in the investigator's opinion must have adequate literacy to complete the protocol-specified questionnaires. If a caregiver cannot continue, 1 caregiver replacement is allowed.
6. Male patients:
 - a. agree to use a reliable method of birth control during the study and 3 months following the last dose of the study drug. Acceptable methods of birth control may include: 1) condom with spermicide; 2) diaphragm with spermicide; or 3) female condom with spermicide.
7. Female patients:
 - a. Women of child-bearing potential may participate in the study if they test negative for pregnancy (based on a serum pregnancy test) prior to initiation of treatment. They must also agree to use either 1 highly effective method of contraception or a combination of 2 effective methods of contraception during the study.

Highly effective method may include hormonal contraceptives (e.g., combined oral contraceptives, patch, vaginal ring, injectables, and implants); intrauterine device or intrauterine system; vasectomy and tubal ligation.

Effective methods may include barrier methods of contraception (e.g., male condom, female condom, cervical cap, diaphragm, contraceptive sponge).

Women may choose to use a double-barrier method of contraception. Barrier methods without concomitant use of a spermicide are not reliable or an acceptable

method. Thus, each barrier method must include use of a spermicide. It should be noted that the use of male and female condoms as a double-barrier method is not considered acceptable due to the high failure rate when these methods are combined.

- Women not of child-bearing potential may participate in the study and include those who have
 - a. spontaneous amenorrhea for at least 12 months, not induced by a medical condition such as anorexia nervosa and not taking medications that induced amenorrhea (e.g., oral contraceptives, hormones, gonadotropin-releasing hormone, anti-estrogens, selective estrogen receptor modulators, or chemotherapy; or
 - b. spontaneous amenorrhea for 6 to 12 months and a follicle-stimulating hormone (FSH) level greater than 40 mIU/mL; or
 - c. women with a history of hysterectomy or bilateral oophorectomy must be at least 40 years of age and FSH >40 mIU/mL.
- 8. Are on a stable diet and exercise regimen for >2 months prior to Visit 1.

6.2. Exclusion Criteria

Patients will be excluded from study enrollment if they meet any of the following criteria at screening:

9. Are Eli Lilly and Company, GLWL Research Inc. (sponsor hereafter), contract research organization employees, investigator or site personnel directly affiliated with this study and their immediate families. Immediate family is defined as a spouse, parent, child or sibling, whether biological or legally adopted.
10. Are currently enrolled in any other clinical trial involving a study drug or off-label use of a drug or device, or any other type of medical research judged not to be scientifically or medically compatible with this study.
11. Participated in a clinical trial within 30 days (defined as last dose of study drug), prior to the GLWL-PWS first dose.
12. Are currently living in a group home for more than 50% of the time.
13. Have a HQ-CT total score at Visit 3 <13.
14. Have clinical laboratory test results outside normal reference range, or any clinically significant laboratory abnormality, that in the judgment of the investigator, indicates a medical problem that would preclude study participation. Values for aspartate aminotransferase (AST)/alanine aminotransferase (ALT)/gamma-glutamyl transferase (GGT)/alkaline phosphatase (ALP) >3X upper limit of normal (ULN).
15. Have an estimated glomerular filtration rate <60 mL/minute/1.73 m². Have macroalbuminuria (defined as spot urine albumin to creatinine ratio of >300 µg/mg) or hematuria.
16. Are hypertensive (defined as sitting systolic BP ≥140 mmHg and diastolic BP ≥90 mmHg) on or off medications for the treatment of hypertension. Blood pressure may be re-tested up to 2 additional times, under well-rested conditions.

17. In addition to conditions described below, have a history or presence of any other medical illness including but not limited to any autoimmune disorder, cardiovascular, hepatic, respiratory, hematological, or uncontrolled neurological disease.

- a. Have a history of clinically overt uncontrolled or untreated endocrine illness such as growth hormone insufficiency, adrenal gland, or thyroid illness.
- b. Have evidence of other chronic liver disease, including but not limited to chronic alcoholic disease, cirrhosis of any cause, recent history (within 3 months of screening) of acute viral hepatitis or chronic autoimmune hepatitis. Patients with a history of biliary disease, including primary sclerosing cholangitis, must be excluded. Patients with a history of cholecystectomy longer than 6 months prior to screening could be enrolled.
- c. Have evidence of significant active or unstable/uncontrolled psychiatric disease by medical history, such as bipolar disorder, schizophrenia, personality disorders, or other serious mood or anxiety disorders. Note: Patients whose disease state is considered stable and expected to remain stable throughout the course of the study, in the opinion of the investigator, may be considered for inclusion if they are not on excluded medications.

18. Have an abnormality in the 12-lead electrocardiogram (ECG), including corrected QT interval with Frederica's correction ($QTcF$) >450 msec for men and >470 msec for women or an abnormality that, in the opinion of the investigator, increases the risks associated with participating in the study. If $QTcF$ does not meet criteria, ECGs may be repeated once after 5 minutes of rest.

19. Have a family history of Long QT Syndrome.

20. Have evidence of human immunodeficiency virus (HIV) infection, hepatitis B, hepatitis C and/or positive results at screening for the respective antibodies for HIV, hepatitis B surface antigen, or hepatitis C antibodies.

21. Patients who, in the clinician's judgment, are actively suicidal and therefore deemed to be at significant risk for suicide, or those who have answered "yes" to either Question 4 (Active Suicidal Ideation with Some Intent to Act, Without Specific Plan) or Question 5 (Active Suicidal Ideation with Specific Plan and Intent) on the "Suicidal Ideation" portion of the Columbia–Suicide Severity Rating Scale (C–SSRS), or answer "yes" to any of the suicide-related behaviors (actual attempt, interrupted attempt, aborted attempt, preparatory act or behavior) on the "Suicidal Behavior" portion of the C–SSRS; and the ideation or behavior occurred within a month of Visit 1.

22. Patients on weight loss medications within 30 days of dosing. Patients with a history of bariatric surgery should also be excluded.

23. Unable to refrain from or anticipates the use of

- a. Any drugs known to be significant inhibitors of cytochrome P450 (CYP)3A enzymes and/or P-glycoprotein (P-gp) including regular consumption of grapefruit or grapefruit juice for 14 days prior to the first dose of study medication and throughout the study. Appropriate sources will be consulted

by the principal investigator (PI) or designee to confirm lack of PK or pharmacodynamic (PD) interaction with study medication. Acetaminophen (up to 2 g per 24-hour period) may be permitted during the study.

- b. Any drugs known to be significant inducers of CYP3A enzymes and/or P-gp, including St. John's Wort, for 28 days prior to the first dose of study medication and throughout the study. Appropriate sources will be consulted by the PI or designee to confirm lack of PK/PD interaction with study medication.
- c. Any medications that prolong the QT/QTc interval, unless the patient has been on a stable dose of said medication for at least 3 months and has a QTc <450 msec at Visit 1 and Visit 3.

24. Currently taking simvastatin >10 mg per day, atorvastatin >20 mg per day, or lovastatin >20 mg per day. The doses of these statins in combination products should not exceed these defined dose levels. Patients with a history of statin-induced myopathy/rhabdomyolysis should also be excluded.

25. Current smokers, or any use of tobacco and nicotine products within 3 months of dosing.

26. Regular user of known drugs of abuse and/or shows positive findings on urinary drug screening.

27. An average weekly alcohol intake that exceeds 21 units per week (males \leq 65 years of age) and 14 units per week (females and males $>$ 65 years of age), or is unwilling to stop alcohol consumption for the duration of the study (1 unit = 12 oz or 360 mL of beer; 5 oz or 150 mL of wine; 1.5 oz or 45 mL of distilled spirits).

28. Venous access insufficient to allow for blood sampling as per the protocol.

29. Any major surgery within 60 days prior to the first dose or has planned elective surgeries to occur during the study.

30. Unsuitable for inclusion in the study in the opinion of the investigator.

6.3. Lifestyle Restrictions

Consumption of foods and beverages containing the following substances will be limited or prohibited as indicated:

- xanthine/caffeine: throughout the study, patients are required to maintain their regular intake of caffeinated beverages for the duration of the study
- Alcohol: an average weekly alcohol intake should not exceed 21 units per week (males \leq 65 years of age) and 14 units per week (females and males $>$ 65 years of age).
- Grapefruit/Seville orange: 14 days before first dosing and throughout the study.

Following the morning dose on Day 14 and Day 42, and on Day 84 and Day 112, patients will remain ambulatory or seated upright for the first 4 hours, except when they are supine or semi-reclined for study procedures.

Patients will be instructed to refrain from strenuous physical activity which could cause muscle aches or injury, including contact sports at any time from Visit 1 until completion of the study

participation. Patients should otherwise minimize changes in their activity levels during study participation.

6.4. Screen Failures

Patients who do not meet the criteria for participation in this study (screen failure) at Visit 1 may be rescreened. Individuals may be rescreened up to 1 time. The rescreen should be at the discretion of the PI after discussion with sponsor medical representative. If a rescreening is performed, the individual must sign a new informed consent form (ICF) and will be assigned a new identification number.

7. Treatments

7.1. Treatments Administered

GLWL-01 drug product is supplied for clinical trial use as size 0 dark blue opaque capsules for oral administration. Capsules will contain 150 mg of GLWL-01. No additional excipients are used, with the exception of the capsule itself.

The GLWL-01 drug product placebo will consist of microcrystalline cellulose and magnesium stearate filled directly into size 0 dark blue opaque capsules, identical in appearance to GLWL-01 150-mg capsules.

Capsules must be taken whole.

In Treatment Period 1, all eligible patients will undergo a single-blind (patients/caregiver) placebo lead-in phase, wherein they will receive 3 capsules of placebo BID for 14 days.

Following this, patients will be randomly assigned to either GLWL-01 450 mg BID/placebo or placebo/GLWL-01 450 mg BID treatment sequence. During Treatment Period 1, patients will receive 3 capsules of 150-mg GLWL-01 (450-mg total dose) or identical matching placebo BID for 28 days.

Before Treatment Period 2, patients will undergo a 28-day Washout Period following which all patients will receive 3 capsules of placebo BID during the 14-day single-blind placebo lead-in phase.

During Treatment Period 2 double-blind treatment phase, patients will receive 3 capsules of 150-mg GLWL-01 (450-mg total dose) or identical matching placebo BID for 28 days. The double-blind treatment phases in both treatment periods must not exceed 28 days and patients must not administer the double-blind study drug beyond 28 days. The study drugs can be administered in fed or fasted conditions.

The investigator or designee is responsible for

- explaining the correct use of the study drug to patients and caregivers;
- verifying that instructions are followed properly;
- maintaining accurate records of study drug dispensation and collection;
- and returning all unused medications to sponsor or its designee at the end of the study.

Note: In some cases, sites may destroy the material if, during the investigative site selection, the evaluator has verified and documented that the site has appropriate facilities and written procedures to dispose of clinical materials.

7.1.1. Packaging and Labeling

The sponsor or its designee will provide sufficient quantities of GLWL-01 drug products to allow completion of this study. GLWL-01 drug products are manufactured, tested, packaged, and labeled in accordance with all applicable good manufacturing practice requirements, guidelines, and regulations and will be labeled according to the country's regulatory

requirements. A certificate of release confirming that study drugs are released for human use in clinical trials will be supplied. GLWL-01 drug products are for investigational use only and are to be used only within the context of this study.

7.2. Method of Treatment Assignment

Patients who meet all criteria for enrollment will be randomized 1:1 to 1 of 2 treatment sequences: GLWL-01/placebo or placebo/GLWL-01 (Treatment Period 1 double-blind treatment phase/Treatment Period 2 double-blind treatment phase). Assignment to treatment sequence will be determined by a computer-generated random sequence using an interactive web-response system (IWRS). The IWRS will be used to assign bottles containing study drug to each patient. During the patient's/caregiver's visit, site personnel will access the IWRS for the correct bottle numbers to dispense.

7.2.1. Timing of Dose Administration

The doses should be administered at approximately the same times on each day.

The study drug will be administered at the site on Days 14 and 42 (Treatment Period 1) only.

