The secondary analysis will be conducted similar to the primary analysis. The secondary efficacy endpoint is the CGIC.

Safety: Safety analyses will be conducted on the safety analysis set. Safety data will be summarized by treatment group. Safety parameters that will be assessed include adverse events,

clinical laboratory parameters, C-SSRS, vital signs, electrocardiogram parameters, and weight. The parameters will be listed and summarized using standard descriptive statistics.

Pharmacokinetics/Pharmacodynamics: Plasma GLWL-01 pharmacokinetic (PK) parameters will be calculated using noncompartmental methods after single and multiple dose administration. Additional PK parameters may be calculated if deemed appropriate. Pharmacokinetic parameters will be summarized by dose level using descriptive statistics. Mean and individual GLWL-01 plasma concentration-time curves will be represented graphically.

Pharmacodynamics of GLWL-01 will be based on plasma AG and potentially UAG measures. Raw and change from baseline values will be reported and summarized for AG and potentially UAG.

The PK/PD relationship of GLWL-01 with PD, efficacy, and/or safety measures may be explored.

2. Schedule of Activities

Table GLWL-PWS.1. Schedule of Activities

Period	Screening ^a	Treatment Period 1			Washout (28 days)	Treatment Period 2			Follow-up	ET ^c	
Phase		Single-blind Placebo Lead-in Phase (14 days)	Double-blind Treatment Phase (28 days) ^b				Single-blind Placebo Lead-in (14 days)	Double-blind Treatment Phase (28 days) ^b			
Visit No/ Type Procedure	V1	V2 ^e Phone	V3 ^d	V4	V5	V6 ^e Phone	V7 ^e Phone	V8	V9	V10	V11
Day	-28 to -3	0 (±3)	14 (±2)	21 (±2)	42 (±2)	56 (±2)	70 (±2)	84 (±2)	91 (±2)	112 (±2)	126 (±3)
Informed consent	X										
Demographics	X										
Physical examination ^f	X		X	X	X			X	X	X	X
Height ^g	X										
Initial history/ preexisting conditions	X										
Concomitant medications	X	X	X	X	X	X	X	X	X	X	X
HBsAg, HCAB, HIV	X										
Urinalysis ^h	X										
Substance abuse screen ⁱ	X										
Inclusion/exclusion review	X		X ^e								
Study drug dispensing		X	X				X	X			
Study drug administration at site			X		X						
Study drug accountability			X		X			X		X	X
Efficacy and Outcome Measures											
HQ-CT		X	X	X	X	X	X	X	X	X	X
CGIC					X				X		X
Body weight ^g	X		X		X			X	X	X	X
Percentage fat mass (calipers)			X		X			X	X		X
BMI	X		X		X			X	X	X	X
Waist circumference			X		X			X		X	X
Vital signs ^j	X		X	X	X			X	X	X	X

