Period	Screening ^a	Treatment Period 1				Washout (28 days)	Treatment Period 2			Follow-up	ET ^c	
Phase		Single-blind Placebo Lead-in Phase (14 days)	Double-blind Treatment Phase (28 days) ^b				Single-blind Placebo Lead-in (14 days)	Double-blind Treatment Phase (28 days) ^b				
Visit No/ Type Procedure	V1	V2 ^e Phone	V3 ^d	V4	V5	V6 ^e Phone	V7 ^e Phone	V8	V9	V10	V11	
Day	-28 to -3	0 (±3)	14 (±2)	21 (±2)	42 (±2)	56 (±2)	70 (±2)	84 (±2)	91 (±2)	112 (±2)	126 (±3)	
12-lead ECG ^k	X		X	X	X			X	X	X	X	X
12-lead ECG 2 hours post-dose ^k			X					X				
Serum pregnancy test ^l	X									X		X
Urine pregnancy test ^l			X					X				
Clinical chemistry and hematology ^h	X		X	X	X			X	X	X		X
Troponin			X	X	X			X	X	X		
Lipid panel			X		X			X		X		X
AG and UAG ^m			X		X			X		X		X
Plasma sample collection for PK analysis ⁿ			X		X							X
C-SSRS	X	X	X	X	X	X	X	X	X	X	X	X
Adverse events	X	X	X	X	X	X	X	X	X	X	X	X

Abbreviations: AE = adverse event; AG = acylated-ghrelin; BMI = body mass index; CGIC = Caregiver Global Impression of Change; C-SSRS = Columbia–Suicide Severity Rating Scale; ECG = electrocardiogram; EDC = electronic data capture; ET = early termination; HQ-CT = Hyperphagia Questionnaire for Clinical Trials; HBsAg = hepatitis B surface antigen; HCAB = hepatitis C antibody; HIV = human immunodeficiency virus; PK = pharmacokinetic; UAG = unacylated-ghrelin; V = Visit.

^a Screening visit must occur between -28 days to -3 days of V2.

^b Double-blind Treatment Phase must not exceed 28 days and patients must not take the study drug beyond 28 days. For example, if the V3 occurs on Day 14, then corresponding V5 would occur on Day 42. Similarly, if V3 occurs on Day 15 (Day 14 +1), then corresponding V5 would occur on Day 43 (Day 42 +1).

^c The primary reason for early termination of the patient will be entered in EDC and recorded in the patient's source documents. The patient will attend an early termination visit as soon as possible after participation ceases.

^d Confirm that the patient has met all inclusion/exclusion criteria. Patients will only be dosed after the investigator has completed the appropriate protocol assessments and determined that it is acceptable to dose the patient.

^e Patients/caregivers will receive phone calls from the site; no visit required. Both patient and caregiver should be on the phone in order for the site to conduct AE assessments and the C-SSRS.

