- f A full physical examination with neurological assessments should be performed at Visit 1. Symptom-driven physical examinations should be performed at V3, V4, V5, and V8, V9, V10, V11, and at ET.
- g Height will only be measured at Visit 1. Patients should be instructed to wear lightweight clothing and remove shoes during weighing.
- h Refer to [Appendix 2](#) for details on serum chemistry, hematology, and urinalysis clinical laboratory tests.
- i Substance abuse screen test to be performed at Visit 1 and additionally at any visit per investigator's discretion.
- j Vital sign assessments will include triplicate sitting blood pressure, and single pulse and body temperature. Additional vital sign assessments may be performed as clinically indicated. For visits in which both vital signs and blood samples are collected, vital signs should be obtained prior to blood collection. Any clinically significant result of vital sign assessment will be documented in the source documentation and EDC as an AE.
- k Single 12-lead ECGs to be collected according to the schedule and may be collected at any time if deemed clinically necessary. Patients must be supine for at least 5 minutes prior to ECG collection. When ECG collections are scheduled at the same time point as any other tests, ECGs, followed by vital signs, should be recorded prior to any clinical laboratory or PK blood sampling.
- l For all female patients, the investigator will document potential childbearing status. For women who are postmenopausal, a confirmatory test of serum follicle-stimulating hormone and estradiol levels will be done at Visit 1. For all women of childbearing potential, a pregnancy serum test will be done at Visit 1, which must be negative to enroll. Subsequently, urine pregnancy tests will be done for all women of childbearing potential as indicated in the schedule; the results must be confirmed negative. In case of a positive urine pregnancy test, the serum pregnancy test must be performed to confirm the pregnancy results.
- m The blood samples for AG and UAG should be collected in the fasted state.

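### Protocol 7.2.1 rules out an on-site dose at Visit 8 (Day 84), where the schedule and SAP 7.5 require a 2-hour post-dose ECG: a minor operational safety inconsistency

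*Protocol*

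**What the plan says.** **Where dosing takes place.** Protocol 7.2.1: "The study drug will be administered at the site on Days 14 and 42 (Treatment Period 1) only". In the Schedule of Activities, the row "Study drug administration at site" is marked at Visits 3 and 5 only. These are also the two scheduled visits marked in the row "Plasma sample collection for PK analysis", which otherwise carries a mark only for early termination.

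**When Period 2 double-blind drug reaches the patient.** The row "Study drug dispensing" is marked at Visits 2, 3, 7 and 8. Visit 7 opens the second lead-in, in which, under Protocol 7.1, "all patients will receive 3 capsules of placebo BID during the 14-day single-blind placebo lead-in phase". Visit 8 is therefore the first dispensing of Period 2 double-blind drug. Under Protocol 7.2 it is assigned during the visit: "site personnel will access the IWRS for the correct bottle numbers to dispense".

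**The ECG.** The row "12-lead ECG 2 hours post-dose" is marked at Visits 3 and 8. SAP 7.5 plans the same 2-hour ECG at the baseline of each treatment phase. For the remaining ECGs, footnote k of the schedule says: "Single 12-lead ECGs to be collected according to the schedule and may be collected at any time if deemed clinically necessary". It gives them no time relative to dose.

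**Text pointing to a Day 84 dose.** Protocol 6.3 sets posture rules for the hours after a morning dose on Days 84 and 112, as well as Days 14 and 42. SAP 2.3 makes Study Day 84 the day of the first Period 2 double-blind dose, and its baseline rule relies on the time of that dose.

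**The concern.** An ECG timed at 2 hours after a dose needs a dose, at a known time, while the patient can be recorded. At Visit 8 the schedule asks for the ECG, while 7.2.1 and the dosing row say that no dose is given on site. A site that obeys 7.2.1 either omits the ECG or takes it 2 hours after something other than the first double-blind dose.

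What is at stake is sensitivity to a first-dose peak effect on QTc. Protocol 3.2 reports a median Tmax of about 1 to 2 hours on Day 1 in the earlier type 2 diabetes study, so 2 hours is near the expected first-dose peak. Each patient has one such planned ECG on GLWL-01: at Visit 3 in the GLWL-01/placebo sequence and at Visit 8 in the placebo/GLWL-01 sequence. The protocol also admits patients on stable QT-prolonging medication (exclusion criterion 23c and section 7.7), which gives the reading some added value.

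**Working it through.** The plan gives no figure to reproduce. The check sets the texts side by side and then counts.

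**1. Can both instructions be met at Visit 8?**
- A dose at home before the visit can only be lead-in placebo, because the double-blind bottle is assigned and dispensed at the visit (Protocol 7.1, 7.2 and the dispensing row).
- A dose at the visit is barred by 7.2.1 and is not marked in the on-site row.
- A dose off site after dispensing, with a return for the ECG, is possible in principle but described nowhere.

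As written, then, the two cannot both be met during the visit. The conflict is confined to Day 84. Section 6.3 also mentions Day 112, but no 2-hour ECG is scheduled there.

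**2. Which text is wrong?** Protocol 6.3, the schedule's 2-hour ECG row, SAP 2.3 and SAP 7.5 all fit a Day 84 dose followed by procedures. Only 7.2.1 and the on-site row do not. Because that row marks the same visits as PK sampling, the likeliest cause is a rule written for PK days and not extended when the Visit 8 ECG was added.

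**3. Which patients could be affected on GLWL-01?** One 2-hour ECG on GLWL-01 is planned per patient, and it falls on Day 84 only in the placebo/GLWL-01 sequence.
- Anticipated 19 patients (SAP 2.9), near-equal split: 9/19 = 47.4% or 10/19 = 52.6%.
- Planned 34 patients (Protocol 5.2): 17/34 = 50%.
- With the 10% dropout of Protocol 10.1, all before Day 84: 9 × 0.9 = 8.1 of 18.1 (44.8%), 10 × 0.9 = 9 of 18 (50%), or 17 × 0.9 = 15.3 of 32.3 (47.4%).

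These percentages are mostly the 1:1 allocation restated. They bound how many patients could be affected and do not estimate how often an ECG was missed.

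**4. What would an affected patient lose?**
- Scheduled ECGs after the first GLWL-01 dose and within the double-blind phase: Visit 8 at 2 hours, Visit 9 and Visit 10 = 3. Without the first, 2.
- Of these, ECGs with a set time after dose: 1, falling to 0.
- First on-drug ECG: from 2 hours to a nominal 91 − 84 = 7 days after the first dose. With both ±2-day windows at their limits, the range is 89 − 86 = 3 to 93 − 82 = 11 days.

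In the GLWL-01/placebo sequence, the Visit 8 ECG at risk is the one on placebo.

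**5. Baseline rule.** SAP 2.3 keeps an ECG timed after the dose out of the baseline. An ECG without a time falls to SAP 2.4, which treats an untimed Day 14 or Day 84 ECG as pre-dose and makes no explicit exception for the 2-hour recording. The number affected is unknown and probably small.

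**The case against.** The strongest reply is that the plan, read as a whole, already tells a site what to do. It schedules a post-dose ECG at a visit where drug is dispensed, section 6.3 describes conduct after a Day 84 dose, and the SAP dates the first Period 2 dose to that day. Most sites would probably dose on site, which leaves one sentence and one row that were not updated. This largely stands and is why the point is minor. It does not remove the conflict: none of those texts says that the dose is given at the site, and 7.2.1 says *only*.

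A reader might infer that the placebo/GLWL-01 sequence loses its near-peak ECG, or that about half of these safety ECGs are missing. The documents do not support that. No missed ECG is shown, the loss depends on literal compliance with 7.2.1, and an off-site dose with a return is not excluded. Even in that case, the Visit 9 and 10 ECGs, troponin at Visits 8 to 10 and the QTc stopping rule in Protocol 8 remain. Two hours is also not the only informative time: Protocol 3.2 gives a Day 28 Tmax of about 1 to 4.5 hours.

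A reader might also infer an analysis flaw. There is none. SAP 7.5 counts patients with any post-baseline QTcF value of interest, so patients with later ECGs still contribute. SAP 7 plans no statistical tests on safety endpoints. The concentration-QTcF plot in SAP 9 is little affected, because scheduled PK sampling is in Period 1 only.

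On SAP 2.4, it can be said that the rule assumes assessments happened as planned, and the 2-hour ECG is planned after dosing. That is a fair reading, but the sentence can also be applied the other way.

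Finally, the schedule's marks are read from extracted text, so the on-site row should not be weighed as strong separate evidence. The sentence in 7.2.1 stands without it.

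**Conclusion.** The inconsistency is real and sits in current text: 7.2.1 and the on-site row are wrong for a safety assessment that the schedule and SAP 7.5 require. It is a minor operational safety matter. If 7.2.1 was followed literally, at most about half of patients (9 or 10 of the anticipated 19) would lack their only scheduled on-drug ECG with a set time after dose, and their first on-drug ECG would come a nominal 7 days after the first dose.

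This rests on a near-equal split between sequences, on literal compliance with 7.2.1, and on the Day 1 Tmax from the earlier diabetes study for calling 2 hours near-peak. How often an ECG was in fact missed or mistimed cannot be told from the documents.

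**What to change.** 1. **Protocol 7.2.1 and the on-site administration row:** add Day 84 (Visit 8). State that the dose comes from the bottle dispensed at that visit, that its time is recorded, and that the 2-hour ECG follows it. Protocol 9.5.1 asks for dose times on PK days, and Day 84 is not one.
2. **Study report:** for patients already past Day 84, report by treatment and period how many 2-hour ECGs followed a documented double-blind dose. Enrollment had stopped by the time of the SAP, so the protocol edit may reach few patients and this count may be the more useful step.
3. **SAP 2.4:** classify an untimed Day 14 or Day 84 ECG by its nominal time point, so that an untimed 2-hour ECG cannot become the pre-dose baseline.

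The cost is two short protocol edits, one observed dose at a visit that already exists (the ECG already implies the 2-hour stay), one count and one SAP sentence.
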